The potential research participant will be assessed for medical eligibility by the research team's neurosurgeon, cardiologist and study physician. The study physician will conduct a medical history and physical examination and determine medical eligibility based on the clinical inclusion criteria (#1-4, see section IV.A below) and exclusion criteria (#1-6, see section IV.A below) and consideration of the risk assessment specific for the individual based on their medical history and examination. Following medical clearance for the assessments and participation in the screening portion of the study by the study physician, the potential research participant will undergo behavioral, neurophysiological, and cardiovascular assessments (Appendix #1). Pre-usual care assessments may also be done during the screening visit to reduce the number of study visits for participants who do not live locally. Potential study eligibility will be determined by the investigators based on the evaluation of these assessments to be consistent with the inclusion criteria (#5-9, see section IV.A below). The research participant will then be seen by the study cardiologist who will review the medical record and the cardiovascular assessments. The study neurosurgeon will then review their medical history and the MRI and provide a preliminary recommendation for surgical implantation. *Drug/Nicotine Testing:* The intent is to avoid nicotine users. If a potential research participant tests positive for nicotine during the screening period or the post-usual care/pre-implant assessments, they will be ineligible for the study. After implantation, we will conduct random nicotine testing using a urine sample and levels will be recorded. Nicotine testing will then be done daily until levels are negligible and then weekly for one month. If nicotine levels remain absent, testing will return to random testing. The individual will not be removed from the study after implantation but nicotine levels will be monitored and if detected, levels will be recorded.

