[name] and/or [name] will meet with the potential research participant at the end of the screening and review the results of the assessments and discuss their eligibility. If they are ineligible, the reasons will be explained and they will be asked if they would like to remain in the database for recruitment in future studies. If they are eligible, then all the potential risks will be discussed with them. They will be informed that if they are still interested in participating in the study the next phase is for them to continue with their current daily activities for at least 80 days without any intervention (Usual Care). In some cases an additional pregnancy test may be done if the pre-screen and screen time points are more than 6 months apart.

2. Usual Care (3rd Consent). If the individual is determined to be eligible for the Usual Care period of the study, as determined by the screening assessments, he/she will be consented for Usual Care. The Usual Care period will last for at least 80 days without any intervention and the participant will continue with his/her current daily activities. [name] will encourage the research participant to discuss the study with family, friends, and physicians during this period to facilitate their ability to reach the most informed decision regarding surgical implantation and full enrollment into the study. They will be informed that they are not consenting to surgical implantation – that consent would be signed when they return for the surgical implant and intervention phase of the study. They will also be informed that during the Usual Care phase of the study they can decide not to continue on with the study and let us know at any time. At the completion of the Usual Care phase of the study they will complete the post-usual care behavioral, cardiovascular, respiratory, bladder, bowel, and sexual function assessments (Appendix #1). If the individual meets all the inclusion and exclusion criteria, and is given medical clearance by the study from the cardiologist and the study physician and is recommended for possible implantation by the study neurosurgeon, then they will be enrolled in the study and randomized.

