3. Surgical Implantation and Interventions (4th consent). If the research participant decides to enroll in the surgical implantation and intervention phases of the study, the research participant will return to the Kentucky Spinal Cord Injury Research Center. [name] and/or [name] will meet with the potential research participant to discuss the potential risks of the study and explain that the assessments they

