conducted to determine eligibility for the Usual Care phase of the study will be repeated. Also, the medical eligibility and assessments will be reviewed by the investigators to determine eligibility for surgical implantation and the interventional phase of the study. The research participant will sign the consent form for surgical implantation and intervention and then complete the pre-implant assessments (Appendix #1). The research participant will be assessed by the research team's neurosurgeon, cardiologist and study physician. The neurosurgeon will review all aspects of the surgery including the potential risks specific to the surgery and the medical device with the individual. [name] (study neurosurgeon), [name] (study cardiologist), or [name] (back-up study neurosurgeon) will review the results and collaborate on whether the individual is medically eligible. [name], [name], and/or [name], will review the results and collaborate on whether the individual is scientifically eligible for the study. The physicians will provide a medical recommendation for surgical implantation and participating in the interventional phase of the study. [name] and/or [name] will meet with the potential research participant at the end of the pre-implant assessments and review the results of the assessments and discuss their eligibility. If any new information is identified that would determine they are now ineligible, the reasons will be explained and they will be asked if they would like to remain in the database for recruitment in future studies. If they are eligible, then all the potential risks will be discussed again. [name] and/or [name] will answer any questions the potential research participant or family members may have in relation to the research. They then will be asked whether they would like to participate in the spinal cord implantation and intervention phase of the study. They will be told they can take more time to make their decision if needed. If they decide not to continue on with the study they can let us know and there will be no penalty. They can remain in our database, if desired, for recruitment in future studies.

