Each participant begins 80 sessions of Usual Care to obtain baseline levels, followed by two intervention periods. In the first intervention period (intervention 1, at least 80 sessions), participants will be randomized to one of the four different interventions (A1, A2, B1, or B2). Each research participant will complete at least 80 sessions of the intervention to which they are randomized. At the completion of at least 80 sessions of intervention 1, clinical and neurophysiological assessments will be conducted (Appendix #1). Some assessments may be completed more often.

At the conclusion of the first intervention period, a second intervention period of at least 80 sessions will be commenced. During this second intervention period, participants that had not been receiving weight bearing stand training will be crossed over to receive it. Participants who had been receiving weight bearing training will repeat their current intervention. Thus, participants who had A1 or A2 in intervention 1 would cross over to B1 or B2, respectively, while participants who had B1 or B2 would repeat their intervention.

In what follows it is often convenient to refer to groups (the specific cohort of 9 participants) by their initial intervention in period 1, thus we will refer to groups as A1, A2, B1, or B2, as appropriate.

After at least 80 sessions of the second intervention are completed, assessments are conducted. If an individual does not complete at least 80 sessions of their assigned group intervention, their data will still be evaluated.

Table 1. Interventions for research participants (n=36)

(n=18) Group A		(n=18) Group B	
Intervention #1			
N=9 A1 Vol- scES 6 hours	N=9 A2 CV-scES 6 hours	N=9 B1 Vol-scES 6 hours and Stand-scES + weight bearing training 2 hours	N=9 B2 CV-scES 6 hours and Stand-scES + weight bearing training 2 hours
Intervention #2			
B1 Vol-scES 6 hours and Stand-scES + weight bearing training 2 hours	B2 CV-scES 6 hours and Stand-scES + weight bearing training 2 hours	B1 Vol-scES 6 hours and Stand-scES + weight bearing training 2 hours	B2 CV-scES 6 hours and Stand-scES + weight bearing training 2 hours
Home and Community Integration			

Appendix #1 gives a detailed outline for the timeline and procedures for an individual research participant.

The research participant will be given the choice to have the implant removed by the study neurosurgeon. The neurosurgeon will remove the stimulator if requested by the research participant.

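### Randomising at the end of Usual Care, before surgical consent, the final eligibility decision and the implant, turns losses at those steps into post-randomisation losses

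*Protocol*

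**What the plan says.** Section III.B.2 (Usual Care, 3rd Consent) sets the allocation point. A participant who meets the criteria, is cleared by the cardiologist and study physician, and is recommended by the neurosurgeon for possible implantation is allocated there: "then they will be enrolled in the study and randomized". The same section says of people in Usual Care: "They will be informed that they are not consenting to surgical implantation". That consent is to be signed when they return for the implant phase.

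Section III.B.3 (4th consent) comes next and opens with an open choice: "If the research participant decides to enroll in the surgical implantation and intervention phases of the study". It then provides that:
- eligibility is looked at afresh: "the medical eligibility and assessments will be reviewed by the investigators to determine eligibility for surgical implantation and the interventional phase of the study";
- the 4th consent is given at this stage, not earlier: "The research participant will sign the consent form for surgical implantation and intervention and then complete the pre-implant assessments";
- exclusion is still possible: "If any new information is identified that would determine they are now ineligible";
- an eligible participant is asked again whether to go ahead, may take more time, and may decline without penalty.

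Section III.B.1.c adds that anyone who "tests positive for nicotine during the screening period or the post-usual care/pre-implant assessments, they will be ineligible for the study".

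Surgery, 2-3 weeks of recovery at home, post-implant assessments and mapping follow (III.B.3.a and III.B.3.b). Section III.B.4 says: "In the first intervention period (intervention 1, at least 80 sessions), participants will be randomized to one of the four different interventions". Section III.B names minimisation as the allocation method and aims for 36 participants who complete.

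**The concern.** A person can be assigned to A1, A2, B1 or B2 before agreeing to surgery or to any intervention, and before the team has finally decided that they may have it. Anyone who then refuses, becomes ineligible or is lost through surgery has been randomised but never treated, and has no post-intervention outcome.

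Two things are at stake. The first is the randomised comparison. Dropping such people leaves an analysis set that is no longer the randomised one, while keeping them leaves missing outcomes. The second is the balance that minimisation is meant to give. A lost participant either stays in the running totals and distorts later allocations, or is removed after having already influenced them.

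Loss could also depend on the arm. Group B adds two one-hour stand-training sessions on five days a week (III.E.4), whereas Group A trains largely at home once stable (III.E.2, III.E.3). The protocol states no concealment of the arm before the surgical consent or the final eligibility decision.

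**Working it through.** **Order of events, as printed**

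1. Post-usual-care assessments and clearance, then enrolment and randomisation (III.B.2).
2. Decision whether to enter the implant phase; 4th consent; pre-implant assessments; medical and scientific review; possible ineligibility; last chance to decline (III.B.3).
3. Implant surgery and 2-3 weeks of recovery (III.B.3.a).
4. Post-implant assessments, mapping and configuration (III.B.3.b).
5. Session 1 of the assigned intervention.

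**Where the arm is first needed.** Section III.B.3.a describes one electrode array and one stimulator for everybody. Nothing in steps 2 and 3 depends on the arm. Step 4 is less clear. Section III.B.3.b has configurations for voluntary movement, standing and blood pressure all found before the assigned intervention starts. Section III.B.4, however, has configurations for interventions not received identified after the study. Section III.E.1 lets mapping continue throughout, and III.E.2 and III.E.3 place the search for configurations within each intervention. The arm is therefore not needed before the end of recovery, and it may or may not be needed during configuration.

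**Size of the loss.** The protocol gives no loss rate between randomisation and the first session, so q is assumed. Inputs: 36 participants in four arms of 9 (III.B.4), with losses independent and unrelated to arm.

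- Expected loss = 36 × q
- P(at least one lost) = 1 − (1 − q)^36
- P(some arm loses two or more) = 1 − [(1 − q)^9 + 9q(1 − q)^8]^4

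| Assumed q | Expected lost of 36 | P(at least one lost) | P(some arm of 9 loses ≥2) |
|---|---|---|---|
| 1% | 0.36 | 30% | 1.4% |
| 5% | 1.8 | 84% | 26% |
| 10% | 3.6 | 98% | 64% |
| 20% | 7.2 | over 99% | 96% |

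Worked line for q = 10%: (0.9)^9 = 0.387 and 9 × 0.1 × (0.9)^8 = 0.387. They sum to 0.775, and 1 − 0.775^4 = 0.64.

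Keeping 36 under the present order means randomising 36/(1 − q): 38 at 5%, 40 at 10%, 45 at 20%.

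**Is power the problem?** The only power figure is in III.G: 90% for an effect of 1.7, one-sided 0.05. By the normal approximation, power = Φ(1.7 × √(n/2) − 1.645). At n = 6 per group this is Φ(2.944 − 1.645) = 90.3%, which reproduces the stated figure. At n = 9 it is 97.5%. At n = 7, after two losses in each arm, it is 93.8% (91.1% with the t distribution). Modest loss does not take power below the stated level for that effect, so the harm is selective loss and broken balance.

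**Which tests are exposed.** Section III.G analyses 1a-1c with paired t-tests against baseline, which do not compare randomised arms. The contrasts for 1d-1f, 2a, 2b, 3a and 3b draw on differences between arms.

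**The case against.** **The two sets of assessments may be one visit.** Section III.B.1.c writes the post-usual-care and pre-implant assessments as a single time point, and Appendix #1 has only a pre-implant column. The reviews in III.B.2 and III.B.3 may then be one review described twice, with the 4th consent signed before allocation. A reader might infer that the nicotine test certainly follows randomisation; the documents do not establish this, and ongoing nicotine use is already an exclusion criterion. What stands is that III.B.2 places surgical consent in the future while randomising now, and that the last chance to decline, the surgery and the recovery come later on either reading.

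**Section III.B.4 may seem to contradict III.B.2 on timing.** It does not clearly do so. It says which interventions people are randomised to in period 1, not when the allocation is made.

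**Allocation could simply be moved to after mapping, at no cost.** The documents do not support that as it stands. Mapping has no defined end, and if configuration is arm-specific, allocating afterwards would mean configuring every function for everyone.

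**The harm may be small.** The primary tests are within-participant. The participants have by then given three consents and completed at least 80 days of Usual Care, so a loss near 1% is possible. Bias needs loss related to the arm, and the protocol does not say when anyone learns it. All of this is fair, and influence through knowledge of the arm is possible under the text, not shown. Section IV.E allows a request for more enrolment to reach 36 data sets, written beside withdrawal for noncompliance. That would restore the count but not the randomised comparison. The rule in III.B.4 that incomplete training data are still evaluated does not help with someone never implanted.

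**Conclusion.** The point holds in a limited form. As written, allocation precedes the surgical and intervention consent, the final eligibility decision, the last chance to decline, surgery and recovery, and none of these needs the arm. The losses that the plan permits there are avoidable post-randomisation losses.

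Their size is unknown: about 0.4 to 7 of 36 for an assumed 1% to 20%, taking losses as independent. The exposure is imbalance in arms of 9 and possible bias in the between-arm secondary hypotheses, which are what the randomisation serves.

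A reader might go further and infer that the primary efficacy result is biased by this, that large losses are to be expected, or that power collapses. The documents support none of these. Tests 1a-1c would lose participants but do not rest on randomisation, no loss rate is given, and power for the stated effect survives modest loss.

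**What to change.** In III.B.2, end the sentence at enrolment and remove the randomisation from it. In III.B.3 and III.B.4, state that minimisation is run only after the 4th consent is signed and the final medical and scientific eligibility decision is recorded. Preferably it should also follow implant, recovery and the post-implant/pre-intervention assessments, and be run immediately before any arm-specific configuration or training begins.

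Reconcile III.B.3.b, III.B.4 and III.E.1-III.E.3 on whether configurations for all functions are found before the assigned intervention. If they are, allocation can wait until that work is done; if configuration is arm-specific, allocation should come just before it.

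The cost is a wording change and a later allocation call. Placed before any arm-specific work, it adds no visits or patients. The small downside is that participants learn their arm later and, under the preferred timing, have the implant before knowing it.

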Hypothesis 1a: Primary Efficacy Hypothesis: CV-scES will result in greater cardiovascular functional improvements than those achieved during Usual Care Intervention.

Hypothesis 1b: Secondary Efficacy Hypothesis: Task specific voluntary movement training using Vol-scES will result in greater improvements in voluntary movement than those achieved during Usual Care Intervention.

Hypothesis 1c: Secondary Efficacy Hypothesis: Stand Stand-scES (parameters optimized for standing) will result in greater improvements in the ability to stand than those achieved during the Usual Care Intervention.

Secondary Analyses:

Hypothesis 1d: Task specific voluntary movement training using Vol-scES (parameters optimized for voluntary movement) will result in more successful voluntary movements than CV-scES.

Rationale: We propose that the spinal circuitry is the key integrator of complex signals from the periphery and supraspinal centers that drive the final motor pool output. We predict that the circuitry is continuously adapting to activity-dependent events that functionally configure the spinal networks to optimize generation of a specific motor task. Other possibilities are that the scES retrogradely stimulates residual axons that anatomically cross the lesion but are not functional, or, that scES restores the conduction properties that are lost with demyelination or other consequences of damage [2, 70, 73-76]. If only the restoration of the conduction of the residual supraspinal connections are needed, then the scES **alone** without voluntary training should be sufficient to restore voluntary movement of the legs. However, if the spinal cord circuitry is a key controller, then task specific training of voluntary movement in the presence of scES would also be required to optimally generate voluntary movement.

Methods: Linear statistical models will be fit with coefficients relating to the three stimulation methods. This hypothesis will be tested by if the Vol-scES estimates are significantly higher than those for CV-scES or Stand-scES stimulation parameters. See Section G for details.

Hypothesis 1e: CV-scES (parameters optimized for cardiovascular function) will result in greater cardiovascular functional improvements than Vol-scES.

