For those participants not achieving independent standing during the stand training phase of the protocol, the home and community integration will include training in a customized standing device. Standing devices will be designed to match the level of assistance required to safely translate the training to the home environment. This phase can also include training of care givers or personal trainers to assist the participants in achieving safe and independent standing.

G. Statistical approaches.

For the primary aims (comparing to baseline), paired sample t-tests will be used the primary endpoints (hypotheses 1a, 1b, 1c) comparing the results at the end of the second intervention period to the baseline period.

For the secondary aims, each endpoint will be analyzed separately with a common linear model framework. We fit a linear model with effects for each stimulation setting (voluntary, cardiovascular, and standing) and an effect of weight bearing stand training within each stimulation setting. Thus, for example we have a coefficient which measures the additional benefit of weight bearing stand training and a stimulation setting over and above that stimulation setting alone. There are separate coefficients for the benefit of stand training within Vol-scES, CV-scES, and Stand-scES. Formally, we fit a linear model of the form

$$\begin{aligned} \text{Response} = & \beta_{\text{Vol-scES}} I_{\text{Vol-scES}} + \beta_{\text{CV-scES}} I_{\text{CV-scES}} + \beta_{\text{Stand-scES}} I_{\text{Stand-scES}} + \\ & \beta_{\text{VT}} I_{\text{Vol-scES and Training}} + \beta_{\text{CVT}} I_{\text{CV-scES and training}} + \\ & \beta_{\text{ST}} I_{\text{Stand-scES and training}} + \text{error} \end{aligned}$$

where the β terms give the regression coefficients and I_X is an indicator variable equal to 1 if X occurs and 0 otherwise. The indicator variables function to only include the coefficients of the model for treatments the participant actually receives. Thus, for a participant receiving CV-scES and stand training, the model would reduce to

$$\text{Response} = \beta_{\text{CV-scES}} + \beta_{\text{CVT}} + \text{error}$$

Due to the partial crossover, no carryover effects are included in the model (sensitivity analyses using only the first period data will also be summarized). Random effects for each subject may be included when appropriate.

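### Hypotheses 1a–1c claim improvement beyond that seen during Usual Care, but the stated test only compares the end of period 2 with an unspecified baseline visit

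*Protocol*

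**What the plan says.** Section III.C, Specific Aim 1, lists three hypotheses under its primary analyses. Hypothesis 1a, the primary efficacy hypothesis, states that "CV-scES will result in greater cardiovascular functional improvements than those achieved during Usual Care Intervention". Hypothesis 1b says that voluntary training with Vol-scES "will result in greater improvements in voluntary movement than those achieved during Usual Care Intervention", and 1c says that Stand-scES "will result in greater improvements in the ability to stand than those achieved during the Usual Care Intervention".

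Section III.G assigns the test: "For the primary aims (comparing to baseline), paired sample t-tests will be used the primary endpoints (hypotheses 1a, 1b, 1c". The same sentence then defines which two quantities each test sets against each other, namely by "comparing the results at the end of the second intervention period to the baseline period".

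On the role of Usual Care, Section III.B.4 says "Each participant begins 80 sessions of Usual Care to obtain baseline levels, followed by two intervention periods". Section III.B.2 says "The Usual Care period will last for at least 80 days without any intervention", and then "At the completion of the Usual Care phase of the study they will complete the post-usual care behavioral, cardiovascular, respiratory" and other assessments. Usual Care therefore has an assessment at each end, at least for some outcomes. In Appendix 1 these are the Pre-Usual Care and Pre-implant columns.

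All four randomized interventions in Section III.B.4 (A1, A2, B1, B2) include stimulation.

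**The concern.** The hypotheses set one improvement against another: the gain under stimulation has to exceed the gain over the untreated period. The test sets one level against another. Nothing in the protocol subtracts the Usual Care change, and with stimulation in every arm there is no concurrent control for time effects either. The only control in the trial for practice on repeated testing, changes in other care or regression to the mean is the Usual Care change, and the stated test leaves it out.

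The protocol itself gives a reason to take this seriously for 1a. Participants are selected for cardiovascular dysfunction, including low or highly variable blood pressure (Section IV.A, inclusion criterion 7). Section III.B.1.c allows Pre-Usual Care assessments to be done at the screening visit. If that visit is the baseline, values used for selection may also serve as the starting point, and some apparent recovery would be expected without treatment.

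At stake is what a positive primary result may be said to show.

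**Working it through.** **Which figures the protocol gives.** No power or error rate is stated for the paired tests of 1a–1c. The 90% power at effect size 1.7 in Section III.G concerns comparisons between stimulation settings and does not enter here.

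**Two quantities.** Let U be the Pre-Usual Care value, B the Pre-Implant value, P1 the value after intervention 1 and P2 the value after intervention 2.

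- Hypothesis as worded: gain under stimulation minus (B − U) is greater than 0.
- Test as stated: P2 − B, or P2 − U, is greater than 0. Section III.G does not say which visit represents the baseline period.

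Neither version of the stated test contains the Usual Care change as a comparator. If baseline is U, the Usual Care change is counted as treatment gain.

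**Inputs for an illustration.**

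- n = 18: the participants on CV-scES (A2 and B2, 9 each, Table 1). This is an assumption, because Section III.G does not define the analysis set. It does not carry over to 1c, since by the end of period 2 all 36 have received Stand-scES.
- Drift g = 0.1 or 0.2 SD per period, the same in Usual Care and in each intervention period, with no stimulation effect: an assumption.
- Correlation r = 0.3, 0.5 or 0.7 between any two visits, with equal variances: an assumption.
- Sidedness is not stated for 1a–1c. One-sided 0.05 appears for the between-stimulation comparisons and for echocardiography. Both one-sided 0.05 and two-sided 5% are shown.

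**Formula.** The SD of P2 − B is √(2(1 − r)) in units of the outcome SD. Over k periods the non-centrality is k·g·√n / √(2(1 − r)), with 17 degrees of freedom and critical values 1.740 (one-sided 0.05) and 2.110 (two-sided 5%).

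Example: r = 0.5, g = 0.2, k = 2 gives SD 1.0 and non-centrality 0.4 × √18 = 1.70. The rejection rate is 49% one-sided.

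**Results with Pre-Implant as baseline (k = 2), g = 0.1 / 0.2:**

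| r | One-sided 0.05 | Two-sided 5%, favourable side |
|---|---|---|
| 0.3 | 17% / 39% | 10% / 27% |
| 0.5 | 20% / 49% | 12% / 36% |
| 0.7 | 28% / 68% | 18% / 54% |

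With Pre-Usual Care as baseline (k = 3), the one-sided rates rise to 34% / 79% at r = 0.5 and 47% / 93% at r = 0.7. With zero drift the stated test holds its nominal level under either baseline.

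**The change-versus-change alternative.** For (P1 − B) − (B − U) = P1 − 2B + U, the variance is (1 + 4 + 1) + 2r(−2 + 1 − 2) = 6(1 − r), against 2(1 − r) for the simple difference. The SD ratio is √3 = 1.73. In a simulation of 60,000 runs per setting (n = 9 and 18, r = 0.5 and 0.7, drift 0 to 0.3 SD), this contrast rejected in about 5% of runs at every drift. For a true effect of 0.8 SD with n = 18 and one-sided 0.05, moving to it lowers power from 95% to 59% at r = 0.5, and from 99% to 78% at r = 0.7.

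**Which outcomes allow it.** As Appendix 1 reads:

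- Pre-Usual Care and Pre-implant both scheduled: orthostatic stress test, echocardiography, pulse wave velocity, FNPA, stand independence.
- Pre-Usual Care but no Pre-implant entry: ambulatory blood pressure, NRS.
- Starting only after implant: lower extremity torque, Neuromuscular Voluntary Movement Assessments.

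**The case against.** The best defence is that this is loose wording. Section III.G labels these aims as comparisons with baseline, and Section III.B.4 says Usual Care exists to supply baseline levels. On that reading Usual Care is simply the baseline condition, and a paired level test is a legitimate choice. Much of this stands: the level test need not be replaced. It does not rescue the claim, because all three hypotheses speak of improvements achieved during Usual Care, and the test cannot speak to those.

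A reader might infer that any drift would count as success. It would not. Only favourable drift inflates the success rate; adverse drift works against the treatment.

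A reader might also take the upper rates as the trial's expected error. The documents do not support that. Participants have non-progressive injury, are at least 2 years post injury and medically stable, and cannot stand independently (Section IV.A). Spontaneous gain on the outcomes for 1b and 1c may be close to nil. The cardiovascular outcomes of 1a are more exposed.

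Finally, a reader might conclude that the change-versus-change contrast should become the primary test. It loses considerable power and moves the endpoint from the end of period 2 to the end of period 1. It also removes drift only if the intervals match, and they do not match exactly. Usual Care lasts at least 80 days. The intervention interval adds surgery and 2–3 weeks of recovery (Section III.B.3.a). Stand training at 5 days per week takes 80 / 5 = 16 weeks, or 112 days, if each training day is one session.

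**Conclusion.** The concern holds as a mismatch between claim and test, in the protocol's own words and on its primary hypothesis. It does not depend on any assumed number. As written, a significant paired test supports improvement over baseline, not improvement greater than that under Usual Care, and the baseline visit is left open.

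The consequence can be illustrated but not estimated. The range of 17%–68% one-sided (10%–54% on the favourable side at two-sided 5%) rests on n = 18, equal drift of 0.1–0.2 SD in each of two periods, correlation 0.3–0.7 and Pre-Implant as baseline. None of the drift, the correlation, the analysis set or the sidedness is fixed by the document for these tests. The rates are errors against the hypothesis as worded. As a test of change from baseline, the paired t-test is not at fault.

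**What to change.** 1. Reword 1a–1c as change from the end of Usual Care, so that claim and test agree.
2. In Section III.G, name Pre-Implant as the baseline visit for outcomes scheduled there (for example orthostatic stress test, echocardiography, pulse wave velocity, FNPA, stand independence).
3. Beside each result for 1a–1c, report the Usual Care change (Pre-Implant minus Pre-Usual Care) with its confidence interval, where both visits exist.
4. For ambulatory blood pressure and NRS, which have no Pre-Implant entry in Appendix 1 as read, name Pre-Usual Care as the baseline, word the claim to match, and state that no Usual Care change can be formed. For torque and the Neuromuscular Voluntary Movement Assessments, make no claim against Usual Care.
5. For outcomes measured at all three visits, add the within-participant contrast (Post-Intervention #1 minus Pre-Implant) minus (Pre-Implant minus Pre-Usual Care) as a sensitivity analysis. State its lower precision, its earlier time point and the unequal intervals.

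The cost is an edit to the hypotheses and Section III.G, with no new data and no loss of power in the main test. Items 1 to 3 do not remove drift from the test; they limit the claim and let the reader see the drift that was observed. The downside is a more modest claim.
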